Monofocal lenses correct only at the target distance chosen (i.e., distance without intermediate or near vision improvement or near without distance improvement). Intermediate vision has become important for many daily activities such as reading a mobile phone or tablet. Tecnis Eyhance IOL, recently approved by the FDA,^A is a new generation of monofocal lenses designed to improve and/or enhance intermediate vision without compromising the distance vision with low incidence of halo, glare or starburst. Auffarth et al¹ in a study that included 67 patients implanted bilaterally with the Eyhance IOL showed an improvement of 1 line of intermediate visual acuity compared to a standard monofocal IOL (ZCB00). Additionally, they reported no differences between the 2 groups in contrast sensitivity and visual disturbances complains.

The purpose of this study is to evaluate the visual outcomes of a monofocal IOL with an enhanced intermediate function, in patients with or without astigmatism, when both eyes are targeted for emmetropia and when the non-dominant eye is targeted for mini monovision (-0.75 D) in patients undergoing routine cataract surgery.

1. OBJECTIVE:

CONFIDENTIAL

The main objective of this study is to evaluate the visual outcomes of a monofocal IOL with an enhanced intermediate function, in patients with or without astigmatism, when both eyes are targeted for emmetropia and when the non-dominant eye is targeted for mini monovision (-0.75 D) in patients undergoing routine cataract surgery.

2. STUDY DESIGN AND METHODS:

- A. Test article: Tecnis Eyhance Intraocular lens Toric (DIUxxx) and non-toric (DIB00)
- **B. Study Design:** Prospective, multicenter (up to 2 sites in USA), randomized, patient-masked bilateral eye study.
- C. **Subjects:** A total of 74 subjects who met the Inclusion/Exclusion criteria will be enrolled.

1. Inclusion Criteria:

Subjects **MUST** fulfill the following conditions to qualify for enrollment into the trial

- 1. Subject is undergoing bilateral cataract extraction with intraocular lens implantation.
- 2. Gender: Males and Females.
- 3. Age: 50 years and older.
- 4. Willing and able to provide written informed consent for participation in the study
- 5. Willing and able to comply with scheduled visits and other study procedures.
- 6. Scheduled to undergo standard cataract surgery in both eyes within 6 30 days between surgeries.
- 7. Subjects who require an IOL power in the range of +5.0 D to +34.0 D only.
- 8. Potential postoperative visual acuity of 0.2 logMAR (20/32 Snellen) or better in both eyes.

2. Exclusion Criteria:

Subjects with ANY of the following conditions on the eligibility exam may NOT be enrolled into the trial.

- Severe preoperative ocular pathology: amblyopia, rubella cataract, proliferative diabetic
 retinopathy, shallow anterior chamber, macular edema, retinal detachment, aniridia or iris
 atrophy, uveitis, history of iritis, iris neovascularization, medically uncontrolled glaucoma,
 microphthalmos or macrophthalmos, optic nerve atrophy, macular degeneration (with
 anticipated best postoperative visual acuity less than 20/30), advanced glaucomatous
 damage, etc.
- 2. Uncontrolled diabetes.
- 3. Use of any systemic or topical drug known to interfere with visual performance.
- 4. Contact lens use during the active treatment portion of the trial.
- 5. Any concurrent infectious/non-infectious conjunctivitis, keratitis or uveitis.
- 6. Clinically significant corneal dystrophy.
- 7. Irregular astigmatism.
- 8. History of chronic intraocular inflammation.
- 9. History of retinal detachment.
- 10. Pseudoexfoliation syndrome or any other condition that has the potential to weaken the zonules.
- 11. Previous intraocular surgery.
- 12. Previous refractive surgery.
- 13. Previous keratoplasty
- 14. Severe dry eye
- 15. Pupil abnormalities

16. Subject who may reasonably be expected to require a secondary surgical intervention at any time during the study (other than YAG capsulotomy, i.e. LASIK)

4

- 17. Anesthesia other than topical anesthesia (i.e. retrobulbar, general, etc).
- 18. Any clinically significant, serious or severe medical or psychiatric condition that may increase the risk associated with study participation or may interfere with the interpretation of study results.
- 19. Participation in (or current participation) any ophthalmic investigational drug or ophthalmic device trial within the previous 30 days prior to the start date of this trial.

The principal investigator reserves the right to declare a patient ineligible or non-evaluable based on medical evidence that indicates the patient is unsuitable for the trial.

3. Exclusion Criteria during surgery

If any of the following exclusion criteria are applicable to the study eye, the subject should not continue in the study.

- 1. Other planned ocular surgery procedures, i.e iStent.
- 2. Significant vitreous loss.
- 3. Significant anterior chamber hyphema.

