Potential subjects will be identified from the patients presenting at the clinic. Additionally, an ad will be placed in social media and in the practice website, if deemed necessary. Once identified as a study candidate, the patient will be asked if he/she would like to participate. The sub-investigator, study coordinator or an appropriately trained staff member will answer any and all questions and will obtain informed consent. A copy of the signed informed consent document will be given to the subject. The principal investigator will be available if the subject wants to discuss further details with him. Any testing that is part of the investigative site's standard preoperative cataract evaluation may be performed prior to the informed consent being signed, provided these tests are conducted within 90 days of surgery. The patient will understand that participation in the study, or declining to participate, will not affect his/her quality of care.

No subject will be enrolled into the study that does not meet the inclusion/exclusion criteria and does not sign the current approved informed consent document. Informed consent will be obtained prior to collecting any data for the study. The original signed documents will be maintained by the investigator as a permanent part of the subject's research records.

B. Surgery Procedures:

Patients will be randomized to one of two groups:

- Group A, plano OU. The target refraction for both eyes will be emmetropia (± 0.25 D).
- Group B, mini monovision. The target refraction for the dominant eye will be plano (± 0.25 D) and for the non-dominant eye between -0.75D ±0.15.

C. Study Visit Schedule and Assessments (Table 1).

- **1. Visit Schedule:** Subjects will be examined at the following intervals:
 - 1. Visit 1: Screening and enrollment: Preoperative evaluation completed not more than eight weeks before surgery
 - 2. Visit 2: Day of Surgery
 - 3. Visit 3: Day 1: (12 to 48 hours) after surgery
 - 4. Visit 4: Month 1: 30 ±7 days postoperative after second eye surgery
 - 4. Visit 5: Month 3: 90 ±15 days postoperative after second eye surgery

D. Measurements and evaluations

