1. Visit 1: Informed consent process will be conducted at this visit. Assessments include best-corrected distance visual acuity (BCDVA, Snellen chart), manifest refraction, intraocular pressure (IOP), corneal topography (if astigmatism correction), eye dominance, slit lamp examination including dilated fundus exam, cataract density and type. Any testing that is part of the site's standard of care preoperative cataract surgery evaluation may be performed prior to the informed consent being signed provided these tests are conducted within 90 days of the surgery and notation of the date performed is entered onto the CRF. The surgeon's standard pre cataract surgery treatment will be used in all his patients

Each subject will be randomized to Group A (emmetropia OU) or B (mini monovision). Randomization will ensure that an equal number of subjects are enrolled in each group.

- Visit 2: The surgeon may use his preferred small incision cataract extraction technique (manual phacoemulsification or laser assisted). The assigned lens will be implanted in the bag. The following information will be captured the day of surgery: phaco technique (manual or laser), lens implanted and power, target refraction for IOL power implanted, additional surgical procedures, intraoperative complications, and any device deficiencies. The surgeon's standard post cataract surgery treatment will be used in all his patients. IOL power changes based on intraoperative aberrometry (i.e., ORA) are not allowed.
- 3. Visit 3: monocular UCVA (Snellen), slit lamp examination, IOP, and lens orientation (if toric lens and deem necessary by the investigator) and any device deficiencies.
- 4. Visit 4: Slit lamp examination, manifest refraction, monocular and binocular UCDVA, BCDVA, UCIVA (at 66 cm), DCIVA (at 66 cm), UCNVA (at 40 cm), and DCNVA (at 40), IOP, IOL orientation (if toric lens) and dilated fundus exam as deemed necessary by the investigator, patient satisfaction, visual symptoms and spectacle independence questionnaires, and any device deficiencies.

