- 5. Visit 5: Slit lamp examination, manifest refraction, binocular UCDVA, BCDVA, UCIVA (at 66 cm), DCIVA (at 66 cm), DCNVA (at 40 cm), DCNVA (at 40), and DCNVA at best distance, binocular low contrast (10%) photopic and mesopic BCDVA, DC binocular defocus curve, IOL orientation (if toric lens) and dilated fundus exam as deemed necessary by the investigator, patient satisfaction, visual symptoms and spectacle independence questionnaires, and any device deficiencies.

DC: distance corrected. DC, for the purpose of this study, is defined as corrected for the target refraction (i.e. emmetropia OU corrected for plano. Mini monovison dominant eye corrected for plano and the non-dominant eye for -0.75).

All adverse events and complaints will be monitored and recorded at all study visits.

Table 1. Visits and Study Assessments

	Visit 1 Screening	Visit 2/2A DOS	Visit 3/3A POD #1	Visit 4 1-Month	Visit 5 3-Month
Informed Consent	Х				
Inclusion/Exclusion	Х				
Demographics/PMH/Ocular history	Х				
Eye dominance	Х				
BCVA (Standard of care, Snellen)	Х				
UCVA (Standard of care, Snellen)			Х		
UCVA ETDRS (4m)				X*	X**
Manifest refraction – Max Plus				Х	Х
BCVA ETDRS (4m)				X*	X**
UCIVA ETDRS (66 cm)				X*	X**
DCIVA ETDRS (66 cm)				X*	X**
UCNVA ETDRS (40 cm)				X*	X**
DCNVA ETDRS (40 cm)				X*	X**
DCNVA at best distance					X**
DCVA Photopic low contrast (10%)					X**
DCVA Mesopic low contrast (10%)					X**
Defocus curve					X**
Intraocular Pressure (Standard of care)	Х		X	Χ	
SLE	Х		X	Χ	Х
Dilated fundus exam	Х			X [‡]	X [‡]
Cataract density / type	Х				
Corneal topography¥	Х				
Intraoperative data		Χ			
Toric IOL position		X^{\dagger}	X [†] ±	X ^{†±}	X [‡]
Questionnaires	Х			Χ	Х
AE/Device deficiencies		Χ	Х	X	Х

X To be performed as scheduled

^{*} Monocular and binocular testing

^{**} Binocular testing only

[‡] To be performed as deem necessary by the investigator.

[†] If toric lens

[¥] If astigmatism correction (toric or corneal arcuates)

DC: distance corrected. DC, for the purpose of this study, is defined as corrected for the target refraction (i.e. emmetropia OU corrected for plano. Mini monovison dominant eye corrected for plano and the non-dominant eye for -0.75).

8

4. Study endpoint criteria

- A. Patient Completion of Study: If a study patient has completed the final visit (Visit 5) of the study, he/she is considered to have completed the study.

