5. STATISTICAL CONSIDERATIONS

A. Sample size

The sample size estimates depend in large part on the standard deviation (SD) for logMAR UCIVA. Assuming a SD of 0.12 (from a previous Eyhance study), for the two-sided t-test (alpha =0.05) for the intermediate visual acuity endpoint, we will need 31 subjects in each group (emmetropia / mini monovision) to detect differences of 0.1 logMAR (1 line difference) with 90% power. Total sample size = 62. Allowing 10 % for the potential confounding factor of having 2 sites, and 10% assumed dropout rate, 74 subjects will be enrolled (37 in each group). Table 2 summarizes the sample size estimate.

Table 2. Sample size estimate.

	TOTAL	Mini monovision	Emmetropia
Sample size	62	31	31
10% multiple sites	6	3	3

10% dropout rate	6	3	3
Total sample size	74	37	37

B. Statistical Analysis

All data will be collected by the site and entered into a database. Subjects will be assigned an ID number. Data analysis will be performed without patient identification. Statistical analysis will be performed using standard descriptive statistics and other tests as deemed appropriate based on the characteristics of the data to be analyzed. All statistical tests will be two-sided and interpreted at a 5% significance level. Comparisons between the groups will be made. Data analysis will be conducted by a third-party consultant.

C. Study Endpoints:

Comparisons between the groups:

1. Primary Endpoints:

Binocular distance-corrected intermediate (66 cm) visual acuity at 3 months. Distance corrected. DC, for the purpose of this study, is defined as corrected for the target refraction (i.e. emmetropia OU corrected for plano. Mini monovison dominant eye corrected for plano and the non-dominant eye for -0.75).

2. Secondary Endpoints:

- 1. Binocular defocus curve at 3 months
- 2. Binocular low contrast distance visual acuity at 3 months
- 3. Uncorrected and distance-corrected near (40 cm) visual acuity at 1 and 3 months
- 4. Uncorrected and distance-corrected intermediate (66 cm) visual acuity at 1 and 3 months
- 5. Uncorrected and best-corrected distance (4 m) visual acuity at 1 and 3 months
- 6. Distance-corrected near visual acuity at best distance at 3 months
- 7. To evaluate patient's overall satisfaction of their vision
- 8. To evaluate patient's spectacle independence
- 9. To evaluate visual symptoms using a questionnaire.
- 10. Residual mean spherical equivalent refraction at 3 months
- 11. Residual refractive sphere at 3 months

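### Does the investigator's power to call a patient non-evaluable, with no analysis set named in Section 5, let randomised patients be dropped once their arm is known?

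*Combined protocol and SAP*

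**What the plan says.** - **Section 2.C.2, closing paragraph.** This concerns the principal investigator, who "reserves the right to declare a patient ineligible or non-evaluable based on medical evidence that indicates the patient is unsuitable for the trial". The list that this paragraph closes is introduced by the words "of the following conditions on the eligibility exam may".
- **Section 3.A.** "No subject will be enrolled into the study that does not meet the inclusion/exclusion criteria".
- **Section 2.C.3.** A separate list covers events during surgery after which the subject should not go on. Its note takes subjects with aborted surgery out of the efficacy analysis. This is the only efficacy exclusion that the document states.
- **Section 4.B and 4.C.** These cover administrative discontinuation, replacement of patients lost before surgery, and termination for a severe adverse event.
- **Section 5.B.** "Comparisons between the groups will be made. Data analysis will be conducted by a third-party consultant". Section 5 names no analysis set.
- **Masking and knowledge of arm.** Section 2.B describes a "randomized, patient-masked bilateral eye study". The arm is defined by target refraction; for Group B in Section 3.B, "The target refraction for the dominant eye will be plano" and the other eye is aimed at mini monovision. The site records "lens implanted and power, target refraction for IOL power implanted" on the day of surgery (Section 3.D, Visit 2). The correction used for the primary measurement also depends on the arm: "Mini monovison dominant eye corrected for plano and the non-dominant eye for -0.75".

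**The concern.** Ineligible and non-evaluable are two words, and the second usually describes a patient's status for analysis. It occurs once, without a definition, a time limit or a stated consequence for the data. Randomisation is described at Visit 1, the site knows the arm from the target refraction, and Section 5 does not say which randomised patients are compared. On the bare text, a patient could be ruled non-evaluable after the arm, and perhaps the acuity, is known.

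At stake is the primary comparison, binocular distance-corrected intermediate acuity at 3 months. Randomisation protects it only if the patients analysed are settled without regard to arm and outcome. Selective removal of poor acuities from one arm would bias the difference and raise the false-positive rate.

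**Working it through.** **Step 1. What the clause governs.** Three features of the text point to eligibility.

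- Position: it closes the list tied to the eligibility exam, and the list for events during surgery follows it as a separate section.
- Test: the standard is whether the patient is unsuitable for the trial, supported by medical evidence. That is a test for entry. It is not a judgement on a measurement.
- Consequence: none is given for the data. In Section 2.C.3, where data are meant to leave the efficacy analysis, the document says so.

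Only the single word non-evaluable supports the other reading.

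**Step 2. The plan's own figures.** Section 5.A gives SD 0.12, difference 0.1 logMAR, two-sided alpha 0.05 and power 90%.

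n per group = 2 × (1.960 + 1.282)² × 0.12² / 0.1² = 30.3, rounded up to 31. This agrees with the plan. With the noncentral t, power at 31 per group is 89.8%. Table 2 adds up: 62 + 6 + 6 = 74, or 37 per group.

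**Step 3. If the wider reading were used.** From the documents: 37 less 3 assumed dropouts gives 34 per group, with SD 0.12. Assumed, and not in the documents: k = 1, 2 or 3 patients removed, all from one arm, with no true difference. Each case is a simulation of 200,000 trials with a two-sample t-test at two-sided 0.05; the Monte Carlo standard error is about 0.05 percentage point.

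| How patients are removed | Type I error, k = 1, 2, 3 | Mean shift (logMAR) |
|---|---|---|
| Unrelated to acuity | 5.0%, 5.0%, 5.0% | none |
| At random from the worse half | 4.9%, 5.2%, 5.8% | 0.003, 0.006, 0.009 |
| At random from the worst quarter (8 of 34) | 5.3%, 6.2%, 8.0% | 0.005, 0.010, 0.015 |
| Exactly the k worst | 6.3%, 8.6%, 12.1% | 0.008, 0.014, 0.020 |

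A hand check of the second row: the mean of the upper half of a normal distribution lies 0.798 SD above the centre, and 0.798 × 0.12 = 0.096. Removing k such values shifts the arm mean by about k × 0.096 / (34 − k), which is 0.003, 0.006 and 0.009.

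**Step 4. Power.** For a difference of 0.1 logMAR, power is 92.3% with 34 v 34 and 91.1% with 34 v 31. Losing three patients from one arm leaves power above the planned 90%.

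**Step 5. Would rewording the clause close the gap?** Not by itself. Suppose the investigator's ruling were confined to the time before the envelope is opened. A randomised patient could still leave by a criterion in Section 2.C.3, by administrative discontinuation (4.B) or by termination (4.C), and none of these is stated to be decided masked. A rule that everyone with a 3-month value is analysed would not reach patients who left before Month 3.

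**The case for a change.** The strongest case for a change is that a screening-only reading leaves the word non-evaluable with nothing to do, because ineligible already covers screening. Some items in the same list also reach past the eligibility exam, such as contact lens use during the active part of the trial and the type of anesthesia used. The safeguards are a third-party analyst, data review by the study manager and statistician (Section 7) and documented deviations (Section 9). None is said to be masked to arm, and none fixes who is analysed. The two-sided error also understates the directional effect: with removals from the worse half, false positives favouring the depleted arm are 3.0%, 3.7% and 4.7%, against a nominal 2.5%. A sentence naming the analysis set would be cheap.

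Much of this stands as description. The word is undefined, Section 5 is silent and the site knows the arm. It does not show that a rule in the plan gives a wrong answer when followed. The directional figures still need every removal to come from one arm and to track poor acuity. Both arms receive the same lens type with different refractive targets, and nothing in the documents shows which arm a site would favour. A low cost is a reason to welcome a clarifying sentence, but it does not make the plan faulty without one.

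**Conclusion.** No change to the plan is needed. The clause most naturally concerns eligibility and removes no one's data. The silence in Section 5 is a gap that the analyst can fill sensibly: all randomised patients with a 3-month binocular value, in their assigned groups, apart from the stated aborted-surgery exclusion, with losses and exclusions reported by group and reason.

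If the wider reading were used, and 1 to 3 patients were removed at random from the worse half of one arm, type I error would be 4.9% to 5.8% and the shift at most 0.009 logMAR, under a tenth of the 0.1 design difference. The 12.1% figure requires exactly the three worst acuities to be removed, all from one arm, each backed by medical evidence. It is an upper bound for three removals.

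These sizes rest on normal acuities with SD 0.12, 34 per group and assumed numbers of removals. The conclusion would change if the completed trial showed randomised patients with 3-month data left out on an investigator's ruling.

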Potential subjects will be identified from the patients presenting at the clinic. Additionally, an ad will be placed in social media and in the practice website, if deemed necessary. Once identified as a study candidate, the patient will be asked if he/she would like to participate. The sub-investigator, study coordinator or an appropriately trained staff member will answer any and all questions and will obtain informed consent. A copy of the signed informed consent document will be given to the subject. The principal investigator will be available if the subject wants to discuss further details with him. Any testing that is part of the investigative site's standard preoperative cataract evaluation may be performed prior to the informed consent being signed, provided these tests are conducted within 90 days of surgery. The patient will understand that participation in the study, or declining to participate, will not affect his/her quality of care.

No subject will be enrolled into the study that does not meet the inclusion/exclusion criteria and does not sign the current approved informed consent document. Informed consent will be obtained prior to collecting any data for the study. The original signed documents will be maintained by the investigator as a permanent part of the subject's research records.

B. Surgery Procedures:

Patients will be randomized to one of two groups:

- Group A, plano OU. The target refraction for both eyes will be emmetropia (± 0.25 D).
- Group B, mini monovision. The target refraction for the dominant eye will be plano (± 0.25 D) and for the non-dominant eye between -0.75D ±0.15.

C. Study Visit Schedule and Assessments (Table 1).

- **1. Visit Schedule:** Subjects will be examined at the following intervals:
 - 1. Visit 1: Screening and enrollment: Preoperative evaluation completed not more than eight weeks before surgery
 - 2. Visit 2: Day of Surgery
 - 3. Visit 3: Day 1: (12 to 48 hours) after surgery
 - 4. Visit 4: Month 1: 30 ±7 days postoperative after second eye surgery
 - 4. Visit 5: Month 3: 90 ±15 days postoperative after second eye surgery

D. Measurements and evaluations

1. Visit 1: Informed consent process will be conducted at this visit. Assessments include best-corrected distance visual acuity (BCDVA, Snellen chart), manifest refraction, intraocular pressure (IOP), corneal topography (if astigmatism correction), eye dominance, slit lamp examination including dilated fundus exam, cataract density and type. Any testing that is part of the site's standard of care preoperative cataract surgery evaluation may be performed prior to the informed consent being signed provided these tests are conducted within 90 days of the surgery and notation of the date performed is entered onto the CRF. The surgeon's standard pre cataract surgery treatment will be used in all his patients

Each subject will be randomized to Group A (emmetropia OU) or B (mini monovision). Randomization will ensure that an equal number of subjects are enrolled in each group.

- Visit 2: The surgeon may use his preferred small incision cataract extraction technique (manual phacoemulsification or laser assisted). The assigned lens will be implanted in the bag. The following information will be captured the day of surgery: phaco technique (manual or laser), lens implanted and power, target refraction for IOL power implanted, additional surgical procedures, intraoperative complications, and any device deficiencies. The surgeon's standard post cataract surgery treatment will be used in all his patients. IOL power changes based on intraoperative aberrometry (i.e., ORA) are not allowed.
- 3. Visit 3: monocular UCVA (Snellen), slit lamp examination, IOP, and lens orientation (if toric lens and deem necessary by the investigator) and any device deficiencies.
- 4. Visit 4: Slit lamp examination, manifest refraction, monocular and binocular UCDVA, BCDVA, UCIVA (at 66 cm), DCIVA (at 66 cm), UCNVA (at 40 cm), and DCNVA (at 40), IOP, IOL orientation (if toric lens) and dilated fundus exam as deemed necessary by the investigator, patient satisfaction, visual symptoms and spectacle independence questionnaires, and any device deficiencies.
- 5. Visit 5: Slit lamp examination, manifest refraction, binocular UCDVA, BCDVA, UCIVA (at 66 cm), DCIVA (at 66 cm), DCNVA (at 40 cm), DCNVA (at 40), and DCNVA at best distance, binocular low contrast (10%) photopic and mesopic BCDVA, DC binocular defocus curve, IOL orientation (if toric lens) and dilated fundus exam as deemed necessary by the investigator, patient satisfaction, visual symptoms and spectacle independence questionnaires, and any device deficiencies.

DC: distance corrected. DC, for the purpose of this study, is defined as corrected for the target refraction (i.e. emmetropia OU corrected for plano. Mini monovison dominant eye corrected for plano and the non-dominant eye for -0.75).

All adverse events and complaints will be monitored and recorded at all study visits.

Table 1. Visits and Study Assessments

	Visit 1 Screening	Visit 2/2A DOS	Visit 3/3A POD #1	Visit 4 1-Month	Visit 5 3-Month
Informed Consent	Х				
Inclusion/Exclusion	Х				
Demographics/PMH/Ocular history	Х				
Eye dominance	Х				
BCVA (Standard of care, Snellen)	Х				
UCVA (Standard of care, Snellen)			Х		
UCVA ETDRS (4m)				X*	X**
Manifest refraction – Max Plus				Х	Х
BCVA ETDRS (4m)				X*	X**
UCIVA ETDRS (66 cm)				X*	X**
DCIVA ETDRS (66 cm)				X*	X**
UCNVA ETDRS (40 cm)				X*	X**
DCNVA ETDRS (40 cm)				X*	X**
DCNVA at best distance					X**
DCVA Photopic low contrast (10%)					X**
DCVA Mesopic low contrast (10%)					X**
Defocus curve					X**
Intraocular Pressure (Standard of care)	Х		X	Χ	
SLE	Х		X	Χ	Х
Dilated fundus exam	Х			X [‡]	X [‡]
Cataract density / type	Х				
Corneal topography¥	Х				
Intraoperative data		Χ			
Toric IOL position		X^{\dagger}	X [†] ±	X ^{†±}	X [‡]
Questionnaires	Х			Χ	Х
AE/Device deficiencies		Χ	Х	X	Х

X To be performed as scheduled

^{*} Monocular and binocular testing

^{**} Binocular testing only

[‡] To be performed as deem necessary by the investigator.

[†] If toric lens

[¥] If astigmatism correction (toric or corneal arcuates)

DC: distance corrected. DC, for the purpose of this study, is defined as corrected for the target refraction (i.e. emmetropia OU corrected for plano. Mini monovison dominant eye corrected for plano and the non-dominant eye for -0.75).

8

4. Study endpoint criteria

- A. Patient Completion of Study: If a study patient has completed the final visit (Visit 5) of the study, he/she is considered to have completed the study.
- B. Patient Discontinuation: Each study patient may voluntarily discontinue the study at any time they choose. Study patients who cannot complete the study for administrative reasons (e.g., non-compliance, failure to meet visit schedule, etc.) will be discontinued from the study. Study patients discontinued during the enrollment phase (prior to surgery) of the study will be replaced.
- C. Patient Termination: A study patient will be terminated if the study patient develops any severe adverse event that may be related to the study. A study patient will receive appropriate treatment at the discretion of the investigator. Notification of termination will be clearly documented. These study patients are considered to have completed the study and will not be replaced.
- D. Study Termination: The investigator with appropriate notification may terminate the study. If, after clinical observations, the investigator feels that it may be unwise to continue the study, he may stop the study.
- E. Study Completion: The study will be complete when all enrolled patients have completed Visit 5 or have been terminated from the study.

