- 12. Residual refractive cylinder at 3 months
- 13. Percentage of eyes with postoperative MRSE accuracy to target ≤ 0.5D at 3 months

D. Safety Analyses

The type, severity, duration and frequency of reported ocular adverse events will be tabulated for each group. Adverse events will also be summarized for events that were considered

[name] 10

treatment-related. Comparison of treatment groups with respect to the proportion of study patients reporting adverse events will be made using Fisher's Exact Test.

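### At Month 3, the final visit, best-corrected acuity is scheduled binocularly only, so a one-eye loss after Month 1 may have no per-eye record at exit

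*Combined protocol and SAP*

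**What the plan says.** **Month 1 (Visit 4).** Section 3.D lists "monocular and binocular UCDVA, BCDVA, UCIVA (at 66 cm), DCIVA (at 66 cm), UCNVA (at 40 cm" and further near tests. Table 1 agrees: the row for best-corrected ETDRS acuity at 4 m carries the mark defined as "Monocular and binocular testing".

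**Month 3 (Visit 5).** Section 3.D lists "Slit lamp examination, manifest refraction, binocular UCDVA, BCDVA, UCIVA (at 66 cm), DCIVA (at 66 cm" and further tests, with no mention of monocular acuity. In Table 1 the same row now carries the mark defined as "Binocular testing only".

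**Exit.** Section 4.A makes Visit 5 the end of participation: "If a study patient has completed the final visit (Visit 5) of the study, he/she is considered to have completed the study".

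**Endpoints and safety.** Secondary endpoint 5 (section 5.C.2) covers best-corrected distance acuity at both 1 and 3 months and does not say whether it is per eye or binocular; endpoints 1 and 2 do say binocular. Endpoint 13 is counted per eye: "Percentage of eyes with postoperative MRSE accuracy to target ≤ 0.5D at 3 months". For safety, section 5.D says: "The type, severity, duration and frequency of reported ocular adverse events will be tabulated for each group". It names no acuity outcome.

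**The concern.** A binocular acuity score tends to follow the better eye. If one eye loses best-corrected vision between Month 1 and Month 3 and the other does not, the only best-corrected value scheduled at exit may barely move.

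The other required per-eye checks at Visit 5 are limited. Intraocular pressure is in neither the Visit 5 text nor the Visit 5 column of Table 1, and the dilated fundus exam is at the investigator's discretion. Slit lamp examination is the only mandatory ocular-health examination. The safety tables count reported events, so a decline that neither patient nor examiner remarks on has no objective route into them.

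The eligibility rules leave room for such a change. Section 2.C excludes macular degeneration only below a stated anticipated acuity, excludes diabetes only when uncontrolled, and allows for a YAG capsulotomy during the study.

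At stake are the completeness of per-eye safety capture at exit, and the ability to report secondary endpoint 5 per eye at both of its time points.

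**Working it through.** **1. Is the Month 3 test really binocular only?** The Visit 5 sentence alone could be read with the word binocular attached only to the first test named. Table 1 settles it.

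| Source | Month 1 | Month 3 |
|---|---|---|
| Section 3.D text | monocular and binocular | binocular; monocular not mentioned |
| Table 1, BCVA ETDRS (4 m) | monocular and binocular | binocular only |

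Text and table agree with each other at each visit, so this is a design gap and not a contradiction.

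**2. How long before exit is the last per-eye value?** Section 3.C gives 30 ± 7 and 90 ± 15 days after second-eye surgery.

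- Month 1 window: 30 − 7 = 23 to 30 + 7 = 37 days.
- Month 3 window: 90 − 15 = 75 to 90 + 15 = 105 days.
- Shortest gap: 75 − 37 = 38 days. Longest: 105 − 23 = 82 days. Nominal: 90 − 30 = 60 days.
- At most 74 × 2 = 148 eyes are concerned.

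**3. How far can a one-eye loss move the binocular score?** The documents give no figure, so this step is illustrative. Assume that both eyes are at 0.0 logMAR at Month 1, the fellow eye stays there, the binocular score is never worse than the better eye, and two equal eyes together gain a summation s of 0 to 0.10 logMAR.

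- Month 1 binocular score: 0.0 − s.
- Month 3 score after a loss of 0.2 or 0.3 in one eye, with all summation lost: 0.0.
- Binocular change: 0.0 − (0.0 − s) = s, that is 0 to 0.10 logMAR, whether the loss was 0.2 or 0.3.

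A 2- to 3-line loss in one eye therefore appears as one line at most, and that line does not identify the eye.

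**4. Does anything else at Visit 5 require a per-eye acuity?**

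| Visit 5 item | Per eye? | Requires an acuity to be recorded? |
|---|---|---|
| Slit lamp | yes | no |
| Manifest refraction | yes, implied by endpoint 13 | no |
| Dilated fundus exam | yes, discretionary | no |
| Questionnaires | no, patient level | no |
| Adverse events and complaints | if noticed | no |

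**5. Is the primary analysis touched?** The primary endpoint (section 5.C.1) is binocular DCIVA at 3 months, compared between randomised groups. It uses no monocular value, so neither the estimate nor its validity depends on one. The sample size does not either. For reference, with SD 0.12, difference 0.1, two-sided alpha 0.05 and 90% power, n = 2 × (1.960 + 1.282)² × 0.12² / 0.1² ≈ 30.3, rounded up to the plan's 31 per group. The exact t-test gives 31.25, and 89.8% power at 31.

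**The case against.** The strongest reply is that a one-eye loss is hard to miss. Each eye is refracted at Visit 5, so the examiner is likely to meet a 2- or 3-line drop during a required procedure. Slit lamp examination is mandatory, and capsular change in particular is looked for there. Symptom and satisfaction questionnaires are given, complaints and adverse events are recorded, and a fundus exam is permitted. Much of this stands: what is missing is a recorded value, not every chance to notice. A reader might infer that late one-eye losses would pass unseen; the documents do not support that. But refraction as scheduled need not yield a recorded acuity, and noticing depends on the examiner.

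Second, both arms receive the same lens, described as FDA-approved, and differ only in refractive target. The documents give no reason to expect late monocular loss to differ by arm, and no endpoint explicitly demands monocular acuity at Month 3. This stands and limits the weight of the point.

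Third, the 38 to 82 days is simply the interval between two visits. Adding a test at Visit 5 does not shorten it; it puts a per-eye measurement at its end. The documents give no rate of late one-eye loss, so the number of eyes affected cannot be sized.

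A reader might also infer that the primary result is weakened, since in Group B any intermediate gain would be expected to come through the non-dominant eye. The documents do not support this. The primary comparison is binocular and randomised, and Month 1 already provides monocular DCIVA and BCDVA. A Month 3 per-eye value would only help interpret an individual poor score: distance correction already sets the non-dominant eye at its target, so the remaining question is whether the target gave little benefit or the eye itself had lost acuity.

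**Conclusion.** The point holds as a gap in safety capture and in per-eye reporting of secondary endpoint 5. Best-corrected acuity is measured in each eye at Month 1 and not at exit, and nothing else at Visit 5 requires a per-eye acuity to be recorded. A loss arising in the 38 to 82 days between the two visits may therefore leave no objective per-eye record.

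The interval and the binocular-only schedule follow directly from the documents. The claim that a 0.2 to 0.3 logMAR one-eye loss shows as no more than 0.10 binocularly rests on an assumed stable fellow eye at 0.0 logMAR and an assumed summation range; with no summation the binocular score would not move at all. How often this would happen among up to 148 eyes is unknown.

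The primary estimate and the sample size are unaffected. This is a cheap improvement, not a flaw that threatens the trial's conclusion.

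**What to change.** - In Table 1, change the Visit 5 mark on the BCVA ETDRS (4 m) row to the one meaning "Monocular and binocular testing", and amend the Visit 5 text in section 3.D to match.
- Record each eye's BCDVA after the manifest refraction already scheduled. The uncorrected and distance-corrected tests can stay binocular.
- State in secondary endpoint 5 that best-corrected distance acuity is reported per eye and binocularly at both visits.
- Add to section 5.D a descriptive per-eye summary of BCDVA change from Month 1 to Month 3, by group and by dominant or non-dominant eye, including the number of eyes losing 0.2 logMAR or more. That cut-off is this review's choice for reporting, is not taken from the documents, and carries no clinical action.
- Leave the dilated fundus exam at the investigator's discretion, as written.

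Cost: two extra readings per patient, a few minutes with chart and staff already in use, plus the matching CRF and database fields and one addition to the safety tables. Sample size and primary analysis do not change.
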